Potential subjects will be approached regarding participation in this study. They will be provided with a written consent form, and allowed adequate time to read the form. After reading, they will

be given a chance to ask questions. If they decide to participate, they will be asked to sign the consent form.

Subjects will then be asked to fill out a health history form. The subjects will then be escorted to a clinical electrical stimulator. We plan to test a variety of skeletal muscles to ensure mastery of the technique. Conductive electrodes will be on the skin at each end of the tested muscle(s). Each subject will have two target muscle groups tested (extensor carpi radialis longus, and tibialis anterior). Each muscle will be stimulated at three separate stimulation frequencies (2 Hz, 4 Hz, and 6Hz) over 3 minutes each, for a total of 9 minutes of stimulation per muscle. The clinical electrical stimulator will then deliver mild electrical stimulations to the muscle (20-100 mA). This intensity of stimulation typically produces only mild discomfort typical of muscle contraction. The clinical stimulator has a maximum output of 110 mA, phase duration 1,000 microseconds, 250 Hz. Any stimulation delivering 25 microcoulombs or higher cannot travel through the thorax because of the risk of cardiac arrhythmias. All stimulations applied in this study will be below this threshold. The stimulation frequencies listed above will be within this safety margin.

The accelerometer used throughout the study will be an Axivity AX3 wireless accelerometer. It will be placed on the muscle belly using double sided tape between the two stimulating electrodes.

Fatigue will be defined as a drop in acceleration from peak acceleration. This will be measured using a triaxial accelerometer over 3 separate stimulation frequencies for a total of 9 minutes of testing per muscle. The device will record 2,160 individual muscle twitches. The highest acceleration over a single muscle twitch will be used as the peak acceleration. The data will then be normalized to this peak acceleration to quantify the percentage of maximal acceleration of each twitch.

The electronic stimulator is currently FDA approved for use in clinical patients so a device determination is not being requested. The accelerometer is passively recording accelerations, with no energy input to the patient. The FDA currently states the following as approved uses for clinical electrical stimulators:

INDICATIONS FOR USE

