1. Relaxation of muscle spasms
2. Prevention or retardation of disuse atrophy
3. Increasing local blood circulation
4. Muscle re-education
5. Immediate post-surgical stimulation of calf muscles to prevent venous thrombosis
6. Maintaining or increasing range of motion

Powered muscle stimulators should only be used under medical supervision for adjunctive therapy for the treatment of medical diseases and conditions. Our intended use for the clinical electrical stimulator is to prevent disuse atrophy.

Risks & Discomforts: The risk of pain or discomfort associated with the use of the stimulator is very small and every effort will be made to minimize this. The electrical stimulation procedure occurs at a very low current (20-40 milli-amperes) and is not typically associated with pain. There may be an unfamiliar sensation as the muscle contracts, but the majority of subjects will not find this to be uncomfortable. In the event a subject does not tolerate the stimulation, testing on that

subject will cease. Patients may decide not to continue with higher frequencies at any point during the study.

Another risk of participation in the study is a breach of confidentiality. Please refer to the 'Data and Safety Monitoring' section below for a description of how your personally identifiable health information will be protected. No personal information, including names or email addresses, will be made available to anyone outside of Grady, Emory or the GSU team.

There are no psychosocial risks anticipated from this study. If the patient is uncomfortable or wishes to terminate their participation in the study at any time, they may do so. This will not affect their health care treatment. Formal removal from the study can be done by contacting any of the individuals overseeing the study or members of the individual's normal care team at Grady.

Potential Benefits: The patient may or may not receive a direct benefit from participating in this study. The anticipated benefits involve helping patients better manage their condition and follow treatment plans. The information gained from the study may help improve care for future patients.

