Data storage: Strict patient confidentiality will be maintained. Data other than the health history forms will be collected via a triaxial accelerometer and downloaded directly to a Georgia State University computer. This data will be stored on the computer and backed up to a digital storage device that is locked inside filing cabinet inside a locked office. Only the researchers listed on this application will have access to the data. Following the completion of this study, data will be maintained on a university computer. Any paper records will be stored in the manner listed above. All patient information will be de-identified prior to post-study analysis.

5. Participant selection

Requested Sample Size: 150 (extra 50 to account for subject drop outs)

Inclusion criteria:

1. Patients ≥ 18 years of age
2. Patients transferred from the ICU to a lower level of care within the past 7 days
3. Mechanical ventilation for greater than 7 days while in the ICU
4. Ability to understand English and provide written consent

Exclusion criteria:

1. Vulnerable populations including: patients who are pregnant or prisoners
2. Patients who are unable to understand English or provide written consent

Subject recruitment plan:

Screening for eligibility: Targeted patients will include those recently transferred from the ICU to a lower level of care within the hospital. Following routine care, patient records will be reviewed and patients will be asked if they are interested in joining this study and if they meet the aforementioned inclusion and exclusion criteria.

Withdrawal from study: Formal removal from the study can be done by contacting any of the individuals overseeing the study or members of the individual's normal care team at Grady. This

can be done at any time without affecting the patient's ability to obtain routine follow-up care from the post-op clinic or care staff.

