Informed consent: Consent will be obtained from patients by a trained research assistant or trained member of the study staff. As mentioned above, patients will be identified as meeting inclusion criteria at the time of transfer from the ICU. If they are eligible, the research assistant will approach them with the opportunity of enrolling in the study. At the time, all potential risks, benefits, and procedures related to participating in the study will be explained as described on the informed consent form. The patients will be given the attached informed consent form and, in the case that they sign it, will begin the on-boarding process for enrollment. All patients have the option to avoid enrollment into the study and can end participation in the study at any time, as described above. Patients will be randomly selected and enrolled by research assistants, rather than directly by the principal investigator, minimizing the risk of coercion.

6. Statistical Analysis

Data will be split into 2 groups (weak vs non-weak) based on clinical strength assessment scores. A 2 factor ANOVA will be used to compare peak acceleration, time to peak acceleration, end acceleration, and fatigue ratio based on group (weak vs non-weak) and stimulation frequency (2 Hz, 4 Hz, 6 Hz). We are collecting 9 minutes of accelerometer data for each muscle, and MRC scores for each subject. A post-hoc analysis with Bonferroni correction will be used to identify where differences occur.

7. Adverse event reporting

The probability of adverse events remains extremely low given the nature of this intervention, but patients can report all events directly to the study staff. Depending on the nature of the event, the individual's participation in the study may be terminated. In the case of a data leak or HIPAA violation, the study staff will jointly address the nature of the leak and determine if any PHI has been leaked. Beyond this, standard HIPAA reporting guidelines will be followed.

8. Data and Safety Monitoring Plan

No personally identifiable (PI) information will be shared with anyone outside of the research team or patient's care team. Any data shared following completion of the study will be de-identified prior to use, protecting the patients' PHI and abiding by the HIPAA Privacy Rules. The only foreseeable disclosure of data beyond the study is in the case of publication of data.

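### Patients may stop before the higher frequencies, but section 6 has no rule for their partial data, so the 4 and 6 Hz group differences can be weakened and stages cut short are not comparable

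*Combined protocol and SAP*

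**What the plan says.** Section 4 (Study Design and Methods) sets the test: "Each muscle will be stimulated at three separate stimulation frequencies (2 Hz, 4 Hz, and 6Hz) over 3 minutes each", on two muscles. On fatigue it says: "Fatigue will be defined as a drop in acceleration from peak acceleration". 

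The Risks & Discomforts text in section 4 gives two routes to an incomplete test. One is intolerance: "In the event a subject does not tolerate the stimulation, testing on that" subject will cease. The other is patient choice: "Patients may decide not to continue with higher frequencies at any point during the study".

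Section 5 (Participant selection) gives the only provision for loss: "Requested Sample Size: 150 (extra 50 to account for subject drop outs").

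Section 6 (Statistical Analysis) says: "A 2 factor ANOVA will be used to compare peak acceleration, time to peak acceleration, end acceleration, and fatigue ratio based on group" and stimulation frequency. It describes the data as complete: "We are collecting 9 minutes of accelerometer data for each muscle, and MRC scores for each subject". It names no analysis set, no rule for a partly tested subject or a stage cut short, no missing-data method, and no report of who stopped and where.

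**The concern.** Permission to decline is specific to the higher frequencies, so the missing data will fall mainly in the 4 and 6 Hz cells of the planned ANOVA. The outcome is the muscle's response to stimulation, and stopping is a response to the same stimulation, so a link between the two is plausible. If there is one, and it acts more on one group, the patients who supply 6 Hz data are a selected part of that group. Extra enrolment restores the number of patients but not the ones who stopped.

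Objectives 1 and 2 look for a fatigue pattern that marks the weak group. Unequal stopping can flatten such a pattern at the higher frequencies.

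A second problem does not depend on selection. A stage that ends early has no 3-minute value. If its last recorded twitch is taken as end acceleration, the muscle has had less time to fatigue and looks more resistant than it is.

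**Working it through.** **The plan's own figures.**
- Sample size: 150 with 50 for drop-outs leaves 100, and 100/(1 − 1/3) = 150. The allowance is 50/150 = 33%. The base of 100 cannot be checked, because no alpha, power, effect size or SD is given.
- Twitches: (2 + 4 + 6) × 180 = 2,160, which matches "The device will record 2,160 individual muscle twitches" for one muscle tested in full. In ascending order, which is implied but not stated, a stop after 2 Hz leaves 2 × 180 = 360 twitches (17%). A stop after 4 Hz leaves (2 + 4) × 180 = 1,080 (50%).

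**Selection: assumed inputs.** The documents give none of these.
- The fatigue ratio is normal with SD 1, and a lower value means more fatigue.
- The true weak minus not-weak difference is −0.5.
- The groups are of equal size (75 and 75), and all 50 allowed losses are missing at 6 Hz.
- Tolerance correlates ρ with the fatigue ratio, and the least tolerant are lost.

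If a share m of a group is lost, the mean of those who remain rises by ρ × s(m), where s(m) = φ(z_m)/(1 − m), z_m is the m-quantile of the standard normal and φ its density. The observed difference is −0.5 + ρ × [s(weak) − s(not weak)].

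**One tolerance threshold for both groups, one third lost overall.** The weak group loses more only because it is more fatigable.

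| ρ | Lost, weak | Lost, not weak | s(weak) | s(not weak) | Observed difference |
|---|---|---|---|---|---|
| 0 | 33% | 33% | 0.545 | 0.545 | −0.50 |
| 0.5 | 38% | 29% | 0.612 | 0.479 | −0.5 + 0.5 × 0.133 = −0.43 |
| 1 | 42% | 24% | 0.678 | 0.415 | −0.5 + 0.263 = −0.24 |

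A simulation with 1,000,000 patients per group gives the same values. For a true −0.3 it gives −0.26 (ρ = 0.5) and −0.14 (ρ = 1). For a true −0.8 it gives −0.69 and −0.38. The difference shrinks in each case and does not change sign.

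**Other splits of the same 50 losses, true −0.5.**
- Equal 33% in each group by the same mechanism: −0.50 at any ρ.
- 50% of weak and 17% of not weak: s = 0.798 and 0.300, giving 0.00 at ρ = 1 and −0.25 at ρ = 0.5.
- All 50 from the weak group (67% of it): s = 1.091, giving +0.59 at ρ = 1 and +0.05 at ρ = 0.5.

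**Precision alone.** At a 0.5 SD difference and two-sided 0.05 (assumed), power is 86.5% with 75 per group and 70.5% with 50 per group. This is the only selection-related cost when stopping is unrelated to fatigue.

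**A stage cut short.** Assume acceleration falls exponentially to 60% of peak at 180 s. At 60 s it stands at 0.6^(60/180) = 0.84. The last twitch then shows a 16% drop where the full stage would show 40%, with no difference in the muscle.

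**The case against.** Four objections have weight.

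**The link is assumed.** Section 4 ties stopping to tolerance and patient choice, not to a fall in twitch acceleration. It expects most subjects to find the stimulation not uncomfortable, so few may stop. This stands, and it is why the point is conditional. Without a table of stops by group, however, nobody could tell harmless loss from harmful loss.

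**The 33% is a whole-study allowance.** The plan does not say what the 50 covers. Sections 4 and 5 also describe general withdrawal by contacting staff. A reader might infer that drop-out is mainly failure to finish the stimulation, or that a third of the weak group and none of the other will miss 6 Hz. The documents support neither. The allowance serves above only as a scale for possible loss.

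**Reversal.** A reader might infer that the fatigue difference could change sign. In the cases run for a true 0.5 SD, that happened only when all 50 losses came from the weak group. With one threshold for both groups the difference shrank and kept its sign. Weakening is what can be supported.

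**The plan is silent on partial data.** It does not say that partial stages are analysed or that stoppers remain in some cells. This is correct, but silence does not remove the problem. If only finishers are analysed, every cell holds the same patients, and the 2 Hz comparison becomes selected too. If partial stages are used as they stand, end acceleration is read at unequal times.

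It is also tempting to make 2 Hz the lead stage. It is the least exposed to refusal, but not fully protected: intolerance ends testing on the subject, so a stop on the first muscle can remove 2 Hz on the second. Leading with it would also demote 1,800 of 2,160 twitches per muscle (2,160 − 360), while Objective 1 asks for patterns of fatigue.

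**Conclusion.** The point holds as a conditional weakness in section 6. The plan permits incomplete testing, answers it with head-count, and analyses the frequencies as if all were complete.

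If stopping is related to fatigue and differs between groups, the 4 and 6 Hz differences can be weakened. A true 0.5 SD reads about 0.24 to 0.43 SD under one common threshold, one third lost, and ρ from 1 to 0.5. Stopping that is unrelated to fatigue, or equal in both groups by the same mechanism, costs precision only. Effect size, group split, share lost and correlation are all assumptions.

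The unequal-time problem is separate. It arises whenever a stage is cut short and its last twitch is used, whatever the reason for stopping. The 84% against 60% example rests on an assumed exponential decline.

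The plan should be changed, because rules set in advance alter the estimates and cost little. Confidence is medium, since the amount of stopping is unknown.

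**What to change.** Leave the right to stop unchanged. Add to section 6:

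1. **Keep completed stages.** Every completed stage from a patient who stops enters the analysis. Such patients are neither excluded nor replaced from the extra enrolment. Use a model with a subject effect that accepts incomplete subjects, for example a mixed model over all available frequencies. This uses a stopper's earlier stages to inform the later comparison. It does not remove bias from causes of stopping that the recorded data do not reflect, which is why item 3 is needed.
2. **Stages cut short.** Compare acceleration at a common elapsed time stated in advance, or treat the stage-end value as missing. Do not use the last recorded twitch. Apply the same rule to the fatigue ratio. A very early common time leaves little fatigue to compare, so the choice needs a reason.
3. **Report stopping.** Tabulate the number and share stopping by group, frequency and muscle. Interpret the 4 and 6 Hz contrasts beside that table, with the 2 Hz contrast shown as the least selected comparison and not as the lead stage.

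The cost is section 6 wording, slightly more analysis work and one more table. No procedure or patient burden is added.

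### Section 6 names a two-factor ANOVA with no patient term or repeated factor, although every patient is measured at all three frequencies; run literally, it uses the wrong error term unless a patient's values are uncorrelated

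*Combined protocol and SAP*

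**What the plan says.** Section 6 (Statistical Analysis) gives the whole model in one sentence. It begins "A 2 factor ANOVA will be used to compare peak acceleration, time to peak acceleration, end acceleration, and fatigue ratio based on group", and the two factors with their levels are "based on group (weak vs non-weak) and stimulation frequency (2 Hz, 4 Hz, 6 Hz". The section adds only Bonferroni-corrected post-hoc comparisons and a reminder of the data: "We are collecting 9 minutes of accelerometer data for each muscle, and MRC scores for each subject". Neither this section nor any other mentions a patient effect, a repeated factor, a covariance structure or a sphericity correction.

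Section 4 (Study Design and Methods) fixes the data structure. "Each subject will have two target muscle groups tested", and "Each muscle will be stimulated at three separate stimulation frequencies (2 Hz, 4 Hz, and 6Hz) over 3 minutes each". Group is set once per patient, from the MRC score. So group varies between patients and frequency varies within them. Muscle, a second within-patient factor, does not appear in section 6.

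Section 4 also says "The highest acceleration over a single muscle twitch will be used as the peak acceleration" and "The data will then be normalized to this peak acceleration to quantify the percentage of maximal acceleration of each twitch". It does not say whether the peak compared in section 6 is the raw or the normalised value.

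**The concern.** A two-factor ANOVA fitted with only group and frequency treats the three stage values of one patient as if they came from three patients. It tests the group effect and the group-by-frequency interaction against the same pooled residual. When values within a patient are correlated, that residual is the wrong yardstick for both tests, and it errs in opposite directions for the two.

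This ANOVA, with the post-hoc comparisons that follow it, is the only planned inference for all four outcomes. Objective 2 looks for group differences that could become diagnostic criteria, and an over-liberal group test can put forward a difference that is not real. Objective 1 looks for fatigue patterns distinct to weak patients, and an over-conservative interaction test can miss one. Bonferroni correction adjusts for the number of comparisons; it does not repair an error term.

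**Working it through.** **Inputs from the documents.** Two groups, three frequencies and two muscles per patient (sections 4 and 6). Sample size 150, of which 50 are extra for dropout (section 5), leaving 150 - 50 = 100. The stated count, "The device will record 2,160 individual muscle twitches", reproduces as (2 + 4 + 6) Hz x 180 s = 2,160 for one muscle, which confirms that all three stages are run on the same muscle of the same patient.

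**Inputs assumed, because the plan does not give them.** Nominal level 5%; one muscle; 50 vs 50 patients; equal variance sigma^2 in both groups and at all frequencies; a common within-patient correlation rho between frequencies, shown over a range.

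**Expected mean squares for the ordinary ANOVA.**
- Residual (300 values - 6 cell means = 294 df): sigma^2
- Group, under the null: sigma^2(1 + 2 rho)
- Group-by-frequency, under the null: sigma^2(1 - rho)

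The residual matches both only at rho = 0.

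**True size, large-sample form.**
- Group: 2[1 - Phi(1.96/sqrt(1 + 2 rho))]. At rho 0.5: 1.96/1.414 = 1.386, giving 16.6%.
- Interaction (2 df): P(chi-square > 5.991/(1 - rho)) = 0.05^(1/(1 - rho)). At rho 0.5: 0.05^2 = 0.25%.

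Formula, with simulation of 20,000 datasets per setting in brackets:

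| rho | Group test | Group-by-frequency test |
|---|---|---|
| -0.2 | 1.1% (1.3%) | 8.2% (8.2%) |
| 0 | 5.0% (5.1%) | 5.0% (5.0%) |
| 0.2 | 9.8% (10.0%) | 2.4% (2.4%) |
| 0.5 | 16.6% (16.3%) | 0.25% (0.25%) |
| 0.7 | 20.6% (20.9%) | under 0.1% (0.01%) |

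With split-plot error terms, both tests reject 4.7-5.3% throughout. With 25 vs 75 patients the ordinary group test rejects 9.7%, 16.6% and 20.9% at rho 0.2, 0.5 and 0.7, so the split matters little while variances are equal. A nominal 95% interval for the group difference covers 1 minus the formula rate: 90%, 83% and 79%.

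**Power for the interaction.** If the group difference changes by an assumed 0.5 SD from 2 to 6 Hz, power with the ordinary vs the split-plot error term is 29% vs 40%, 21% vs 59% and 14% vs 83% at rho 0.2, 0.5 and 0.7.

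**Single-frequency contrasts.** At one frequency each patient contributes one value, so the variance of the group difference does not involve rho and the pooled residual has the right expectation. Simulated size is 4.7-5.4% at every rho when variances are equal. With assumed SDs of 1:2:3 across frequencies it becomes 0%, 3.5% and 16% at 2, 4 and 6 Hz. With each frequency's own variance it returns to 4.8-5.4%.

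**Unequal variances between groups.** With 25 patients at SD 2, 75 at SD 1 and rho 0.2, the ordinary interaction test rejects 14%, which is liberal. With the SDs swapped, the group test rejects 2.3%, which is conservative. A shared covariance does not cure this: at rho 0.3, with the larger SD in the group of 25, the split-plot tests reject 15.1% (group) and 19.6% (interaction).

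**Both muscles pooled in one ordinary ANOVA.** With an assumed patient share of variance of 0.2 or 0.4 and a patient-by-muscle share of 0.1, the group test rejects 19% or 27%.

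**The case against.** The strongest reply is that section 6 leaves the test underspecified and does not state a wrong one. The phrase counts factors; an ANOVA with one between-patient and one repeated factor also has two. This stands. A reader might infer that the sponsor intends an ordinary ANOVA, and the documents do not show that. But they do not show the alternative either, and two analysts could follow the same sentence to opposite conclusions.

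A reader might also infer that positive correlation alone fixes the directions. It does not, as the unequal-variance cases show. The plan gives neither group sizes nor spreads, so the directions hold only under the equal-variance condition.

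A third tempting inference is that normalisation makes the correlation negative, so that the errors run the other way for peak acceleration. That requires section 6 to analyse a peak already scaled to one maximum over all nine minutes, which the plan does not say. Under assumed log-normal peaks, simulated mean correlations were -0.14 to -0.20, but individual pairs ran from -0.38 to 0.10. The reversal is therefore hypothetical.

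Finally, not every post-hoc comparison is spoiled: single-frequency group contrasts keep about 5% when variances are equal. The study is also meant to try out procedures for follow-on work (section 2), which limits the harm. Its results still inform what that work carries forward.

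**Conclusion.** The concern holds in a conditional form. The plan omits the term that its own design requires, and the literal reading gives wrong error rates for the group and interaction tests unless within-patient correlation is zero, which nothing in the documents supports. If variances are equal across groups and frequencies and correlation is positive, the group test is too liberal (about 10%, 16% and 21% at rho 0.2, 0.5 and 0.7) and the group-by-frequency test too conservative (about 2.4%, 0.2-0.3% and under 0.1%). Positive correlation is plausible for raw acceleration but is not given. These sizes rest on an assumed 5% level, one muscle and 100 patients in equal groups. They illustrate the effect and do not predict this trial's error rates. The documents do not establish that an ordinary ANOVA is intended, that the directions hold whatever the variances, or that any outcome is negatively correlated.

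**What to change.** In section 6, replace the two-factor ANOVA wording with text such as:

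*For each outcome and each muscle, one summary value per frequency stage will be analysed with group as a between-patient factor, frequency as a within-patient factor, and their interaction, using a repeated-measures mixed model with unstructured within-patient covariance. Bonferroni contrasts will be taken from this model, with single-frequency contrasts using that frequency's own variance. The variance will be allowed to differ by group if the two groups' spreads differ.*

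A split-plot ANOVA with a sphericity correction is an acceptable alternative, under the same two conditions on variances. The correction is needed: with unequal SDs or correlations across frequencies, the uncorrected split-plot interaction test rejected about 6.6-7.6%. If both muscles enter one model, add a patient-by-muscle term.

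The section should also state whether each outcome is analysed raw or normalised, and over which period the peak is taken. If one stage were at 100% in nearly every patient, an unstructured fit might be unstable.

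The cost is one paragraph and standard software, with no new data. With positive correlation, group p-values become less favourable and intervals wider. Against the split-plot test, the unstructured covariance costs about 1 point of interaction power (58.4% vs 59.4% at rho 0.5 for the 0.5 SD change). Four outcomes by two muscles makes eight models, so the plan should say which set of contrasts the Bonferroni correction covers.

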**ACCELEROMETER MOTION TO MEASURE MUSCLE FATIGUE IN CRITICALLY ILL
PATIENTS**

NCT04166630

Date: May 27, 2019

IRB00109793

1. Full title: Accelerometer motion to measure muscle fatigue in critically ill patients

Short title: ICU Acquired Weakness

Principal Investigator: [name], MPH

Co-Investigators: [name]
[name]

Updated Draft Date: May 27, 2019

2. Introduction and background

The primary purpose of this study is to develop a procedure to identify intensive care unit (ICU) acquired weakness. This condition occurs in a subset of people admitted into the ICU, and is associated with a 30% increased risk of death before discharge from the ICU.¹ There are currently major limitations in the ability to diagnose ICU acquired weakness, making it difficult to study.² The goal is to develop a non-invasive test that can be administered to both responsive and non-responsive patients. The current proposal will focus on replicating the results of previous research using motion detecting accelerometers to measure fatigue in human skeletal muscles (Willingham and McCully). This study is designed to test out the procedures in patients who have been transferred from the ICU to a lower level of care so that follow-on studies can be designed to help mitigate this condition in the ICU.

3. Objectives

Objective 1: To identify patterns of muscle fatigue that are distinct for patients with ICU acquired weakness

Objective 2: To identify differences in accelerometer data that appear only in the ICU acquired weakness group for later use as diagnostic criteria.

Objective 3: To develop a diagnostic tool for identifying ICU acquired weakness earlier in the patient's care.

The procedures outlined in this study will advance this objective by providing data that can be analyzed based on whether the subjects have ICU acquired weakness or not based on the current testing procedures.

4. Study Design and Methods

Subjects will undergo a clinical strength assessments to classify them based on whether they test positive for ICU acquired weakness. Manual muscle testing will be performed based on the medical research council (MRC) score. A score of < 48 will classify the subject was having ICU acquired weakness placing them in the "weak" group. Subjects with scores exceeding 48 will be placed into the "not weak" group.

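### Two muscles are tested in every patient, but the planned ANOVA has no muscle term, no stated per-muscle analysis and no test of whether the weak vs non-weak difference varies by muscle

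*Combined protocol and SAP*

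**What the plan says.** Section 4 (Study Design and Methods) of the combined protocol and SAP sets out the measurements: "Each subject will have two target muscle groups tested (extensor carpi radialis longus, and tibialis anterior". The stimulation schedule follows from there: "Each muscle will be stimulated at three separate stimulation frequencies (2 Hz, 4 Hz, and 6Hz) over 3 minutes each". Group, frequency and muscle are therefore crossed, with both muscles and all three frequencies observed in the same patient.

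Section 6 (Statistical Analysis) names the method and its four outcomes: "A 2 factor ANOVA will be used to compare peak acceleration, time to peak acceleration, end acceleration, and fatigue ratio". The factors listed for that model are two, since outcomes are to be compared "based on group (weak vs non-weak) and stimulation frequency (2 Hz, 4 Hz, 6 Hz". Muscle appears once in that section, in a sentence about data collection: "We are collecting 9 minutes of accelerometer data for each muscle, and MRC scores for each subject". The follow-up step is described next as "A post-hoc analysis with Bonferroni correction will be used to identify where differences occur", with no definition of the family of comparisons.

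In Section 3, Objective 2 is "To identify differences in accelerometer data that appear only in the ICU acquired weakness group for later use as diagnostic criteria", and Objective 3 is a diagnostic tool. No objective asks for a comparison of the two muscles.

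**The concern.** The design has three crossed conditions and the model has two. Read literally, records from the wrist extensor and the tibialis anterior go into one model that does not distinguish them. The text does not say whether they are averaged, stacked or analysed separately, so the choice could be made after the data are seen.

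What is at stake is the use made of the result. A diagnostic criterion would be applied to a recording from a particular muscle, and the plan prespecifies neither an estimate for each muscle nor a test of whether the estimates differ. The Bonferroni step does not supply one, because it locates differences among the factors in the model and muscle is not among them. Nor would a patient term alone, which addresses within-patient correlation but does not estimate a muscle effect or a group by muscle effect.

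**Working it through.** **The plan's own figures.**
- Twitches: 2 × 180 + 4 × 180 + 6 × 180 = 360 + 720 + 1,080 = 2,160. This matches "The device will record 2,160 individual muscle twitches" for one muscle. Two muscles give 4,320 per patient.
- Sample size (Section 5): 150 − 50 = 100 evaluable. No power, effect size, SD, alpha or group split is given, so there is no power calculation to reproduce.

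**Assumed inputs, none of them from the documents.** Two-sided alpha 0.05; within-group SD of 1 in each muscle; between-muscle correlation ρ of 0.2, 0.3 or 0.5; split 50 vs 50, with 30 vs 70 as a variant; a group difference of 0.6 SD. Power is from the noncentral t distribution with 98 degrees of freedom, on one value per patient per muscle.

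**Case A: the two muscles are averaged within patient.** The average has SD √((1+ρ)/2), which is 0.775, 0.806 and 0.866 for the three values of ρ. A difference of 0.6 in one muscle and 0 in the other becomes 0.3, so the standardised effect is 0.3/√((1+ρ)/2) = 0.387, 0.372, 0.346.

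| Analysis | 50 vs 50 | 30 vs 70 |
|---|---|---|
| Affected muscle alone, alpha 0.05 | 84% | 78% |
| Affected muscle, Bonferroni for two muscles (0.025) | 76% | 68% |
| Average, ρ = 0.2 / 0.3 / 0.5 | 48 / 45 / 40% | 42 / 39 / 35% |

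The 0.025 row is the fair comparator, since the affected muscle is not known in advance. It allows for the two muscles only, not for the four outcomes or three frequencies.

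The same formula with other patterns, 50 vs 50:
- 0.6 in both muscles: the average keeps 0.6, the standardised effect is 0.775 to 0.693, and power is 97% to 93%, above the 84% for one muscle.
- 0.6 and 0.3: the average is 0.45, the standardised effect is 0.581 to 0.520, and power is 82% to 73%.

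**Case B: records are stacked without averaging and without a muscle term.** If the muscles differ in level by D SD, half the records lie D/2 above the midpoint and half D/2 below, which adds D²/4 to the error variance. For D = 1 it is 1 + 0.25 = 1.25 (up 25%); for D = 2 it is 1 + 1 = 2 (up 100%). This is an alternative to Case A. In a within-patient average, a level difference common to all patients cancels.

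**Case C: one ANOVA per muscle.** Nothing is diluted. Four outcomes become 4 × 2 = 8 analyses, with no stated rule across muscles. Significance in one muscle and not in the other would still not test a difference between them.

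**Test of group by muscle, which none of the three cases contains.** The within-patient difference between muscles has SD √(2(1−ρ)). With 0.6 in one muscle and 0 in the other, the standardised effect is 0.6/√(2(1−ρ)) = 0.474, 0.507, 0.600. Power at 50 vs 50 and alpha 0.05 is 65%, 71% and 84%.

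**The case against.** The strongest reply is that pooling is inferred. No sentence says the muscles are combined, and one ANOVA per muscle fits the text too. Section 4 describes 9 minutes of testing and 2,160 twitches, both single-muscle figures, and Section 6 mentions data for each muscle directly after the ANOVA. This stands. A reader might infer that a one-muscle signal will be diluted, but the documents support that only if the muscles are pooled.

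A reader might also infer that the trial cannot say which muscle to use. That is too strong: the data are collected by muscle, so the comparison can be made. It is just not planned.

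Three further replies have force:
- Nothing in the documents suggests weakness confined to one muscle, and with similar effects in both, averaging gains power.
- Section 4 normalises twitches to peak acceleration. If that is done within muscle, which the per-muscle twitch count suggests, normalised outcomes lose most of any scale difference. The inflation in Case B then bears mainly on raw measures such as peak acceleration.
- The objectives do not ask for a comparison of muscles, and Section 4 gives mastery of the technique as the reason for testing several. A three-way term would therefore go beyond the stated aims.

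None of this supplies the missing specification. Whichever handling is intended, it is unwritten, and none of them tests group by muscle.

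**Conclusion.** The point holds as a gap in specification: a within-patient condition of the design is absent from the model, no per-muscle analysis is stated, and no planned test asks whether the group difference varies by muscle.

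The cost in power is conditional. With averaging it ranges from a marked loss (40-48% against 76%) when one muscle carries the whole effect to a gain (93-97%) when both carry it equally. The 25-100% variance inflation belongs to stacking and should not be added to the averaging loss, as a reader might be tempted to do. All of these sizes rest on the assumed effect, correlation, level difference, split and alpha, so they show what is at risk and do not predict this trial's power.

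The plan should be changed, because the remedy is the same under every reading and cheap.

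**What to change.** In Section 6, add muscle (extensor carpi radialis longus, tibialis anterior) as a within-patient factor with a group by muscle term, for example in a mixed model with a patient random effect. Keep the overall group effect, so that the gain from an effect common to both muscles is not lost. For each muscle, report the weak vs non-weak difference with its confidence interval. Define the Bonferroni family and include the two muscles in it. A group by muscle by frequency term is optional.

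The cost is one more model term, a table column for muscle and a slightly stricter Bonferroni threshold. No new data are needed, since recordings are already collected for each muscle.
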